ACCORD	Action to Control Cardiovascular Risk in Diabetes
ACCORD-Eye	Action to Control Cardiovascular Risk in Diabetes Eye Trial
ALT	Alanine aminotransferase
anti-VEGF	Anti-Vascular Endothelial Growth Factor
AST	Aspartate aminotransferase
bid	Two times per day
CI	Confidence Interval
CK	Creatine kinase
CST	Central Subfield Thickness
DME	Diabetic Macular Edema
DR	Diabetic Retinopathy
DRCR.net	Diabetic Retinopathy Clinical Research Network
E-ETDRS	Electronic- Early Treatment Diabetic Retinopathy Study
ETDRS	Early Treatment Diabetic Retinopathy Study
FIELD	Fenofibrate Intervention and Event Lowering in Diabetes
HbA1c	Hemoglobin A1c
HR	Hazard Ratio
ICH	International Conference on Harmonization
IRB	Institutional Review Board
JCHR	Jaeb Center for Health Research
NF-kappa B	nuclear factor kappa-light-chain-enhancer of activated B cells
NPDR	Non-Proliferative Diabetic Retinopathy
OCT	Optical Coherence Tomography
PDR	Proliferative Diabetic Retinopathy
PPAR α	Peroxisome Proliferator-Activated Receptor α
PROMINENT	Pemafibrate to Reduce Cardiovascular Outcomes by Reducing Triglycerides in Patients with Diabetes
PRP	Panretinal Photocoagulation
QALY	Quality-Adjusted Life-Year
US	United States
UWF	Ultra-widefield

INTRODUCTION

1.1 Diabetic Retinopathy Complications and Public Health Impact

The age-adjusted incidence of diabetes mellitus in the United States has reportedly doubled in recent history.¹ Estimates suggest that by the year 2040, approximately 642 million individuals worldwide will be affected by this chronic disease.² The increasing global epidemic of diabetes implies an increase in rates of associated vascular complications from diabetes. At present, almost 8 million people in the United States are estimated to have diabetic retinopathy (DR).³ Despite advances in the diagnosis and management of ocular disease in patients with diabetes, eye complications from diabetes mellitus continue to be a leading cause of vision loss and new onset blindness in working-age individuals throughout the United States.^{4,5}

1.2 Preventing DR Onset and Worsening

At this time, the primary method of slowing DR onset and worsening remains that of strict glycemic control and blood pressure control. Results from the Early Treatment Diabetic Retinopathy Study (ETDRS) revealed that better glycemic control inhibits DR worsening among all age groups, type 1 and type 2 diabetes, and all stages of retinopathy.⁶ The United Kingdom Prospective Diabetes Study (UKPDS) and the Action to Control Cardiovascular Risk in Diabetes (ACCORD) Study demonstrated that improved blood glucose control can reduce the risk of developing DR in patients with type 2 diabetes, with the UKPDS additionally showing the benefit of improved blood pressure control.^{7,8} The Diabetes Control and Complications Trial (DCCT) found that intensive therapy, aimed at keeping glycemic levels as close to normal range values as possible, reduced the risk of any DR developing by 76% (95% confidence interval (CI):62% to 85%) among patients with no DR at baseline and slowed the worsening of DR by 54% (95% CI: 39% to 66%) among patients with mild DR at baseline.⁹ The benefits of intensive treatment were sustained for approximately 4 years after the period of intensive glycemic control with a 75% ($P<0.001$) risk reduction in the worsening of DR.¹⁰ This beneficial effect in fact persisted for even as long as 18 and 25 years later in this cohort of study participants with type 1 diabetes.^{11,12} This beneficial effect also persisted in type 2 diabetes.^{13,14}

Despite improvements in systemic glycemic control,¹⁵ there continues to be a substantial proportion of diabetic patients who develop DR and its associated sequelae. In 2005–2008, 28.5% (4.2 million) of Americans with diabetes aged 40 years or older had DR, and of this group, 655,000 individuals had advanced DR that could lead to severe vision loss.¹⁶ Approximately 40-60% of the Wisconsin Epidemiologic Study Diabetic Retinopathy (WESDR) cohort, whose onset of diabetes occurred between 1922 and 1980, developed proliferative diabetic retinopathy (PDR) over time, with rates of visual impairment (vision of 20/40 or less in the better seeing eye) ranging from approximately 5% to 20%.¹⁵

1.3 Limitations of Current Treatments for PDR and DME

Recent advances in therapy for advanced diabetic eye disease include the use of anti-vascular endothelial growth factor (anti-VEGF) agents to prevent vision loss from PDR and also to treat center-involved DME. Anti-VEGF therapy has been shown to be highly effective in treating active ocular neovascularization as well as in increasing visual gain and decreasing visual loss in eyes with center-involved DME.¹⁷⁻¹⁹ However, anti-VEGF treatment does have drawbacks including the need for recurrent intravitreal injections for medication delivery that are performed as often as once a month. These injections have potential associated side effects including the development of endophthalmitis and incremental cost effectiveness ratios when using aflibercept or ranibizumab that are far beyond \$100,000 per Quality-Adjusted Life-Year (QALY) over a 10-year time horizon compared with bevacizumab.²⁰ In addition not all eyes treated with anti-VEGF have resolution of

51 DR or DME.^{19, 21} Scatter laser photocoagulation or panretinal photocoagulation (PRP) is another
52 treatment for PDR that is not invasive and does not need to be repeated as frequently as anti-VEGF
53 injections, but laser treatment has other well-documented adverse effects, including exacerbation or
54 development of macular edema with transient or permanent central vision loss, peripheral visual
55 field defects, night vision loss, loss of contrast sensitivity, potential complications from misdirected
56 or excessive burns, increased risk of vitrectomy compared with anti-VEGF treatment, and
57 worsening of visual loss in nearly 5 percent of individuals despite appropriate treatment.^{19, 22} Thus,
58 there is an ongoing need to identify novel therapies that are both effective for PDR and DME
59 treatment and that also avoid the potential adverse events or costs associated with current ocular
60 interventions. Furthermore, the identification of an oral therapeutic agent that may prevent
61 worsening to PDR or DME might allow treatment of a wider segment of the diabetic population at
62 risk for diabetic eye complications who do not have access to anti-VEGF or laser treatment or who
63 are not suitable candidates for these treatments. This would be a major public health contribution if
64 indeed this potentially effective oral agent could be implemented into clinical care.

65

66 **1.4 Rationale for PPAR α Therapy for DR Worsening**

67 Two major clinical studies in patients with diabetes have demonstrated beneficial effects on ocular
68 outcomes from treatment with oral fenofibrate, which acts via activation of peroxisome proliferator-
69 activated receptor α (PPAR α) and may decrease inflammation through inhibition of NF-kappa B
70 activity.²³ Fenofibrate is an oral medication of the fibrate class with a well-documented and
71 favorable safety profile that is used for treatment of hyperlipidemia. Fenofibrate reduces low-
72 density and very low-density lipoprotein and triglyceride levels while increasing high-density
73 lipoprotein levels. In addition to its agonist effects on the PPAR α pathway, fenofibrate affects
74 human retinal endothelial cells through a PPAR α -independent mechanism. A number of other
75 pathways have also been explored with regards to its effects in diabetic retinopathy. For example,
76 [name] from Harvard has suggested that fenofibrate may inhibit cytochrome P450
77 epoxygenase 2C activity resulting in reduction in pathological ocular angiogenesis, using her
78 oxygen induced retinopathy in a mouse model. Others have suggested a decrease in NF-kappa B
79 activity may be the potential pathway for reduction of diabetic retinopathy progression. Other
80 mechanisms have also been suggested.²⁴⁻²⁹

81

82 The Fenofibrate Intervention and Event Lowering in Diabetes (FIELD) study randomized 9795
83 patients with type 2 diabetes to fenofibrate 200 mg/day versus placebo.³⁰ A subgroup of this cohort
84 (N=1012) also agreed to undergo fundus photography at baseline, 2 year, 5 year, and end of study in
85 order to document DR severity worsening. The percentage of patients requiring first laser treatment
86 for either DR or DME was significantly lower in the fenofibrate group than in the placebo group
87 (3.4% vs 4.9%; HR for first laser treatment: 0.69, 95% CI 0.56-0.84, $P = 0.0002$). 850 participants
88 (84%; 421 allocated to placebo, 429 allocated to fenofibrate) in the photography substudy were
89 followed to the end of the study. Although a difference between the groups overall for the primary
90 endpoint of 2-step DR worsening in the substudy was not identified, in the subgroup of participants
91 with pre-existing DR (N=193), fenofibrate treatment was associated with a reduction in 2-step DR
92 worsening as compared with placebo (3.1% versus 14.6%, $P = 0.004$).

93

94 The Action to Control Cardiovascular Risk in Diabetes (ACCORD) trial enrolled 10,251

Advanced severe NPDR (level 44 to 54, steps 8-9)	101 (3.5)
Severe NPDR or PDR (level 55 to 63, or advanced steps 10-17)	38 (1.4)
Macular edema (non-cystoid)	
None (LME or DME severity 0A)	2579 (82.1)
Mild (1B-1C)	150 (5.3)
Moderate (2-3B)	46 (1.5)
Severe (4-5C)	25 (0.8)
Soft exudates (no total 1+ person)	
None (0 EA)	3570 (90.7)
Very mild (1 EA and <0.02 EA)	117 (3.1)
Mild (≥ 0.03 and <0.12 EA)	128 (3.5)
Moderate (≥ 0.13 EA)	29 (0.7)
Retinal thickening (total 1+ person)	
None (0 EA)	3611 (91.9)
Very mild (1 EA and <0.40 EA)	75 (2.3)
Mild (≥ 0.41 and <1.59 EA)	75 (2.6)
Moderate (≥ 1.60 and <6.25 EA)	49 (1.7)
Severe (≥ 6.26 EA)	12 (0.3)

ACCORD = Action to Control Cardiovascular Risk in Diabetes; EA = due area; ETDRS = Early Treatment Diabetic Retinopathy Study; NPDR = nonproliferative diabetic retinopathy; PDR = proliferative diabetic retinopathy.

156
 157 Table taken from Chew EY, Davis MD, Danis RP, et al. The effects of medical management on the progression of
 158 diabetic retinopathy in persons with type 2 diabetes: the Action to Control Cardiovascular Risk in Diabetes
 159 (ACCORD) Eye Study. *Ophthalmology*. 2014;121(12):2443-51.

161 1.6 Summary of Protocol Rationale

162 Despite improved glycemic and systemic control for many patients with diabetes, over the past
 163 several decades, DR develops and progresses in a large proportion of patients, and visual loss from
 164 diabetic eye complications continues to be a leading cause of blindness in the US and other
 165 developed countries worldwide. Thus, even a modest ability to prevent DR onset or to slow DR
 166 worsening might substantially reduce the number of patients at risk for diabetes-related vision loss

167 worldwide. Widespread use of an oral agent effective at reducing worsening of DR might also
168 decrease the numbers of patients who undergo treatment for DR and DME and who are
169 consequently at risk for side effects that adversely affect visual function. Two major studies of
170 fenofibrate, FIELD and ACCORD-eye, have demonstrated clinically important reduction in
171 progression of retinopathy in patients with diabetes assigned to fibrate compared with placebo.
172 However, despite the positive clinical trial results, fenofibrate has not gained wide acceptance as a
173 preventive agent by either ophthalmologists or primary diabetes care providers. Thus, it is
174 important to provide further evidence demonstrating whether or not selectively increasing PPAR α
175 activity reduces progression of retinopathy in patients with diabetes and non-proliferative diabetic
176 retinopathy at baseline. Pema-fibrate is a more potent and selective PPAR α modulator than
177 fenofibrate. Its efficacy is currently being evaluated in the PROMINENT study for prevention of
178 cardiovascular events in patients with type 2 diabetes. Given the large study cohort with a
179 substantial proportion likely to have DR and the multi-year duration of the PROMINENT trial, this
180 study represents a unique opportunity to assess effects of chronic PPAR α activation through
181 pema-fibrate therapy on DR outcomes.

182

183 **1.7 Study Objective**

184

185 **Primary Objective:**

- 186 1. To assess whether treatment with pema-fibrate (0.2 mg orally BID) compared with placebo
187 reduces the hazard rate of diabetic retinopathy worsening in adults with type 2 diabetes and
188 diabetic retinopathy without neovascularization in at least one eye who are participating in
189 the parent PROMINENT trial.

190

191 **Secondary Objectives:**

- 192 1. To assess whether treatment with pema-fibrate (0.2 mg orally BID) compared with placebo
193 reduces rates of diabetic macular edema development or visual acuity worsening.
- 194 2. To assess whether treatment with pema-fibrate compared with placebo affects safety or
195 tolerability in the cohort of participants with diabetic retinopathy in at least one eye.

196

197

198 **1.8 Study Design and Synopsis of Protocol**

199 **A. Study Design**

200

201

202

203

204

205

206

207

208

209

210

211

212

213

214

215

216

- 200 • Longitudinal ancillary study to the PROMINENT trial.
- 202 **B. Major Eligibility Criteria (see section 2.2 for additional eligibility criteria)**
- 203 • Already randomized at US or Canadian sites in the PROMINENT study
 - 204 a. Enrollment visit into the ancillary study must be conducted within 3 months of
205 randomization into the PROMINENT trial.
 - 206 • Ability to cooperate with dilated ophthalmic examination and imaging procedures
 - 207 • At least one eye meets the following study eye inclusion criteria:
 - 208 a. ETDRS Diabetic Retinopathy Severity level between 20 and 53 (minimal to severe
209 NPDR), inclusive, according to the investigator and confirmed by central Reading
210 Center grading.
 - 211 • Major study eye exclusion criteria are:
 - 212 a. Neovascularization on clinical exam or fundus photographs
 - 213 b. Current central-involved DME based on optical coherence tomography (OCT)
214 central subfield thickness (CST)
 - 215 i. Zeiss Cirrus: CST $\geq 290\mu\text{m}$ in women or $\geq 305\mu\text{m}$ in men
 - 216 ii. Heidelberg Spectralis: CST $\geq 305\mu\text{m}$ in women or $\geq 320\mu\text{m}$ in men

- 217 c. Major non-diabetic intraocular pathology that in the opinion of the investigator
 218 would substantially and adversely affect visual acuity or lead to ocular
 219 neovascularization during the course of the study
 220 d. Anticipated need for intravitreal anti-VEGF, intravitreal corticosteroid, or PRP in
 221 the next 6 months following randomization
 222 e. History of intravitreal anti-VEGF or corticosteroid treatment within the prior year
 223 for any indication.
 224 f. Any history of PRP or vitrectomy
 225

226 Participants may have 1 or 2 study eyes based on how many eyes meet eligibility criteria.
 227

228 **C. Estimated Sample Size**

229 At least 600 individuals are expected to be eligible and to enroll in the study at US and Canadian
 230 DRCR.net clinical sites that have geographic proximity to the parent PROMINENT clinical site.
 231 Recruitment will continue until the PROMINENT trial has completed enrollment, with up to a
 232 maximum of 900 enrolling in PROMINENT-Eye.
 233

234 **D. Protocol Summary**

235 Participants in the parent PROMINENT study will be referred to partnering DRCR.net sites for
 236 comprehensive ophthalmologic examination including visual acuity, fundus photography and
 237 spectral domain optical coherence tomography (OCT) to be performed within 3 months of the
 238 PROMINENT randomization visit. Participants who meet eligibility criteria at this visit will be
 239 eligible for two or three additional study ophthalmic visits through 4 years (see Table in Section E
 240 below). Participants who do not meet ocular eligibility will be discontinued from the ancillary
 241 PROMINENT-Eye Study, but not from the parent study. If intravitreal anti-VEGF or
 242 corticosteroid treatment, PRP, or vitrectomy will be administered to a study eye for any indication
 243 for the first time since entering the study, when possible, all study procedures should be performed
 244 prior to implementing treatment to establish retinopathy severity before therapy is initiated.
 245 Participants who receive treatment will continue follow-up through 4 years.
 246

247 **E. Schedule of Study Visit and Examination Procedures**
 248

Visit and Visit Window	Screening/ Baseline ^a	2 year ^b ± 2 months	4 year ^b ± 2 months ^c	Prior to DME/PDR Treatment Initiation ^d
Best corrected visual acuity	X	X	X	X
Eye Exam ^{e, f}	X	X	X	X
DRCR.net Fundus Photography ^{e, g}	X	X	X	X
Spectral Domain OCT ^e	X	X	X	X
Collection of Adverse Events occurring during the visit	X	X	X	X

249 a. To be performed within 3 months of the PROMINENT randomization visit

250 b. Time from randomization into the PROMINENT trial.

- 251 c. If the PROMINENT trial ends before a participant reaches the 4 year visit, one final visit within 3 months of
252 the PROMINENT trial ending will be completed.
- 253 d. All study procedures should be performed prior to the initiation of treatment for DME or DR in a study eye.
- 254 e. After pupil dilation
- 255 f. Participants may opt out of eye exam particularly if they have recently had an eye exam
- 256 g. The widest camera type available will be used for color fundus photography.

257
258 **F. Outcomes**

259 Primary outcome:

260
261 The primary outcome is diabetic retinopathy worsening or DME development (composite outcome),
262 based on both eyes for bilateral participants and based on the study eye only for unilateral
263 participants. Study eye is defined based on the criteria in section 2.2.2 as the eye(s) having ETDRS
264 Diabetic Retinopathy Severity level between 20 and 53 (minimal to severe NPDR), inclusive,
265 according to the investigator and confirmed by central Reading Center, without definite central
266 subfield involved diabetic macular edema.

267
268 Diabetic retinopathy worsening or DME development is defined as any of the following:

- 269
- 270 • For participants with 2 study eyes: 3-step worsening on the ETDRS Retinopathy Severity Scale
271 for Persons (Table 1 in Section 6) at a protocol visit. This scale takes into account the
272 retinopathy level of both study eyes.
 - 273 • For participants with one study eye: 2-step worsening on the ETDRS Retinopathy Severity
274 Scale for Individual Eyes (Table 2 in Section 6) in the study eye at a protocol visit. This scale
275 only takes into account the retinopathy level of the study eye.
 - 276 • Procedure undertaken for the treatment of PDR at any time (even in the absence of photographic
277 documentation) including PRP, intravitreal anti-VEGF, or vitrectomy in at least one study eye.
 - 278 • Treatment initiated for DME at any time (even in the absence of OCT documentation) including
279 anti-VEGF, corticosteroids, focal/grid laser, or vitrectomy in at least one study eye.
 - 280 • Development of central-involved DME on OCT with vision loss at the 2-year or 4-year visit.
281 Defined as OCT central subfield thickness above the machine and gender-specific thresholds
282 (see Section 2.2.2 for details) with at least a 10% increase in thickness from baseline and visual
283 acuity 20/32 or worse (letter score ≤ 78) in at least one study eye.
- 284

285 Secondary outcomes include a treatment comparison of the following:

286
287 Participant-Level Secondary Outcomes (relates to either eye for bilateral participants and to the
288 study eye for unilateral participants):

- 289
- 290 • Hazard rate of 3-step person-level (for bilateral participants, see Table 1 in Section 6) or 2-step
291 eye-level (for unilateral participants, see Table 2 in Section 6) diabetic retinopathy worsening on
292 the ETDRS Retinopathy Severity Scale or receiving treatment for PDR in at least one study eye
293 at any time (irrespective of DME status or treatment)
 - 294 • Hazard rate of developing central-involved DME on OCT with vision loss (as defined above) or
295 receiving treatment for DME in at least one study eye at any time (irrespective of diabetic
296 retinopathy severity level or treatment)
 - 297 • Person-level diabetic retinopathy severity at 2 years and 4 years
 - 298 • Percentage of participants with at least a 2-line loss in visual acuity from baseline in at least one
299 study eye at 2 years and 4 years

300
301
302
303
304
305
306
307
308
309
310
311
312
313
314
315
316
317
318
319
320
321
322
323
324
325
326
327
328
329
330
331
332
333
334
335
336
337
338
339
340
341
342
343
344

Eye-Level Secondary Outcomes (evaluated only for study eyes):

- Hazard rate of a composite PDR/DME outcome. Defined as the time to 2-step diabetic retinopathy worsening on the ETDRS Retinopathy Severity Scale for Individual Eyes (see Table 2 in Section 6) at 2 years or 4 years, development of central-involved DME on OCT with vision loss (as defined above) at 2 years or 4 years, or treatment for DME or PDR at any time
- Hazard rate of 2-step diabetic retinopathy worsening or receiving treatment for PDR at any time (irrespective of DME status or treatment)
- Hazard rate of developing central-involved DME on OCT with vision loss at 2 years or 4 years or receiving treatment for DME at any time (irrespective of diabetic retinopathy level or treatment)
- Eye-level diabetic retinopathy severity at 2 years and 4 years
- Change in OCT central subfield thickness from baseline at 2 years and 4 years
- Change in visual acuity letter score from baseline at 2 years and 4 years
- Percentage of eyes with at least 2-line loss in visual acuity from baseline at 2 years and 4 years

Safety Outcomes:

- Adverse events collected as part of this ancillary study including vitreous hemorrhage and retinal detachment
- Changes from randomization in ALT, AST, CK, and creatinine

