1.9 General Considerations

The study is being conducted in compliance with the policies described in the DRCR.net Policies document, with the ethical principles that have their origin in the Declaration of Helsinki, with the protocol described herein, and in accordance with ICH E6 Good Clinical Practice. All study investigators will attest to complying with these requirements.

The DRCR.net Procedures Manuals provide details of the imaging procedures.

Retinal images and OCT data will be primary source data, and additional data collected will be directly entered in electronic case report forms, which will be considered the source data.

There is no restriction on the number of participants to be enrolled by a site.

Assessment of adverse events occurring during the Prominent-Eye clinical visit will be obtained through adverse event reporting at the end of each study visit.

A risk-based monitoring approach will be followed, consistent with the FDA “Guidance for Industry Oversight of Clinical Investigations — A Risk-Based Approach to Monitoring” (August 2013).

The risk level for this ancillary research is considered to be no more than minimal risk.

STUDY PARTICIPANT ELIGIBILITY AND ENROLLMENT

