2.2 Subject Eligibility and Exclusion Criteria

2.2.1 Eligibility Criteria

- Already randomized at US or Canadian sites in the PROMINENT study
 - a. Enrollment visit into the ancillary study must be conducted within 3 months of randomization into the PROMINENT trial.
- Ability to cooperate with dilated ophthalmic examination and imaging procedures

2.2.2 Study Eye Criteria:

The study participant must have at least one eye meeting all of the inclusion criteria listed below.

The eligibility criteria for a study eye are as follows (both eyes will be considered study eyes if both meet the eligibility criteria at the time of enrollment):

- At least one eye meets the following study eye inclusion criteria:
 - a. ETDRS Diabetic Retinopathy Severity level between 20 and 53 (minimal to severe NPDR), inclusive, on color fundus photographs confirmed by central Reading Center grading.
- Study eye exclusion criteria are:
 - a. Neovascularization present.
 - b. Current central-involved DME based on optical coherence tomography (OCT) central subfield thickness (CST)
 - i. Zeiss Cirrus: $CST \geq 290\mu\text{m}$ in women or $\geq 305\mu\text{m}$ in men
 - ii. Heidelberg Spectralis: $CST \geq 305\mu\text{m}$ in women or $\geq 320\mu\text{m}$ in men
 - c. Known major non-diabetic intraocular pathology that in the opinion of the investigator would substantially and adversely affect visual acuity or lead to ocular neovascularization during the course of the study

- 393 d. Anticipated need for intravitreal anti-VEGF, intravitreal corticosteroid, or PRP in
394 the next 6 months following randomization
395 e. History of intravitreal anti-VEGF or corticosteroid treatment within the prior year
396 for any indication.
397 f. History of intraocular surgery within prior 4 months or anticipated within the next 6
398 months following randomization
399 g. Any history of PRP or vitrectomy
400 h. History of YAG capsulotomy performed within 2 months prior to screening
401 i. Aphakia
402 j. Known substantial media opacities that would preclude successful imaging
403

404 Participants may have 1 or 2 study eyes based on how many eyes meet eligibility criteria.
405

406 **2.3 Screening Evaluation and Baseline Testing**

407 **2.3.1 Ocular Historical Information**

408 An ocular history will be elicited from the potential study participant including prior ocular
409 diseases, surgeries, and treatment.
410

411 **2.3.2 Baseline Testing Procedures**

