3.1 Visit Schedule

Each participant will have protocol specific follow-up visits scheduled at 2 years (\pm 2 months) and at 4 years (\pm 2 months) from the randomization date in the PROMINENT trial. If the PROMINENT study ends prior to a participant's 4-year visit, the participant will have one closeout visit within 3 months of the last PROMINENT visit.

436 Additional retina evaluation visits may occur as required for usual care of the study participant
437 either by the DRCR.net clinical site or by the participant's non-DRCR.net ophthalmologist. If the
438 participant will be examined by a non-DRCR.net ophthalmologist, the participant will be asked to
439 sign a medical records release so any treatment that is documented can be obtained by the
440 DRCR.net site. In addition, participants for whom ocular treatment for DR or DME is planned for
441 the first time during the trial (e.g. anti-VEGF or corticosteroid intravitreal injection, PRP,
442 focal/grid laser, or vitrectomy) will be asked to return to the DRCR.net clinical site to complete the
443 study procedures before the treatment is administered, provided treatment is not urgently needed as
444 determined by the treating physician. If pre-treatment images are not able to be obtained, study
445 images should try to be obtained within 1 month after treatment initiation. Participants who receive
446 treatment will continue follow-up through 4 years.

447
448 Communication between the PROMINENT clinical site and the PROMINENT-Eye clinical site
449 may occur to facilitate compliance with the follow-up schedule if needed.

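### Vitreous hemorrhage and retinal detachment are safety outcomes to be compared between arms, but the plan collects only adverse events that occur during a study visit and names no source for events between visits

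*Combined protocol and SAP*

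**What the plan says.** Secondary objective 2 (section 1.7) asks whether pemafibrate affects safety or "tolerability in the cohort of participants with diabetic retinopathy in at least one eye". Sections 1.8F and 6.4 both list, as the first safety outcome, "Adverse events collected as part of this ancillary study including vitreous hemorrhage and retinal detachment". Section 6.4 sets one comparison of the ancillary study's safety outcomes, at 4 years, and gives their P-values a separate false discovery rate adjustment. It also plans listings and MedDRA summary tables of adverse events, and for these it refers back to section 4.3 for the definition.

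The collection rule appears three times. The schedule in 1.8E has a row for "Collection of Adverse Events occurring during the visit". Section 1.9 says "Assessment of adverse events occurring during the Prominent-Eye clinical visit will be obtained" by reporting at the end of each visit. Section 4.3 likewise documents events that took place in the course of the visit and passes them to the parent PROMINENT database.

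Scheduled visits after baseline are at 2 and 4 years from parent-trial randomization (or one closeout visit if the parent trial ends first), plus a visit before first ocular treatment when feasible (1.8D, 3.1).

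**The concern.** A visit-day rule suits a minimal-risk imaging study that wants to record reactions to dilation or photography. It does not suit a 4-year drug comparison of two eye events that can begin on any day. A hemorrhage that starts and clears between the 2-year and 4-year visits would not enter the outcome under the stated rule.

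At stake is what the study can say about ocular safety under secondary objective 2. A table with almost no hemorrhages or detachments in either arm could be taken as evidence that such events are rare on treatment, when it would mainly reflect how events were collected.

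**Working it through.** The plan gives no figure to reproduce here. The check is first textual, then a rough sizing.

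**Possible sources for events between visits**

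- *Parent-trial data.* Section 4.3 sends ancillary events to the parent database; no passage describes a return flow. Section 6.3.3 uses parent definitions of deviations and compliance. ALT, AST, CK and creatinine are in the same safety list but have no collection step in 1.8E, so they presumably come from the parent trial. A link therefore looks feasible, but it is not stated for eye events.
- *Outside records.* Under 3.1, participants seen elsewhere are asked to "sign a medical records release so any treatment that is documented can be obtained by the" study site. This covers treatment, not diagnoses.
- *Pre-treatment visit.* Section 1.8D asks for study procedures before the first anti-VEGF, corticosteroid, PRP or vitrectomy in a study eye, whatever the reason for treatment. Section 3.1 and the 1.8E schedule tie the visit to treatment of retinopathy or DME. These passages need to be reconciled. Sections 3.1 and 5.1 waive the visit when treatment is urgent, and the fallback in 3.1 is imaging only: "images should try to be obtained within 1 month after treatment initiation".
- *Examination and photographs.* Footnote f of 1.8E says "Participants may opt out of eye exam particularly if they have recently had an eye exam". Photographs are still taken, and levels 81 and 85 in Table 2 of section 6.1 include vitreous hemorrhage, but no level denotes detachment. No passage says that such a finding counts as an adverse event.
- *Ocular history (4.2).* No visits are named, and there is no question about events since the last visit.
- *Coordinating Center contacts (5.5).* These are optional, roughly six-monthly, and not for adverse events.

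**Literal reading: onset on a visit day**

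The schedule is counted from parent-trial randomization, and 2.2.1 states "Enrollment visit into the ancillary study must be conducted within 3 months of" that randomization. Follow-up from enrollment is therefore 48 months less 0-3 months, or 45-48 months (1370-1461 days). With 2-3 visit days after baseline:

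- lowest share: 2/1461 = 0.14%
- highest share: 3/1370 = 0.22%

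The documents give no incidence. Assume 1-5% of 600 participants have either event, which is 6-30 participants. Expected recorded onsets are 6 × 0.00137 = 0.008 to 30 × 0.00219 = 0.07.

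**Looser reading: a hemorrhage still visible at a scheduled visit counts**

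Assume a hemorrhage is visible for d = 1-6 months and onset is unrelated to visit dates. For follow-up T and two scheduled visits, the share found is f = 2d/T:

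- 2 × 1/48 = 4.2%, and 6 × 0.042 = 0.25 participants
- 2 × 6/45 = 26.7%, and 30 × 0.267 = 8 participants

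If a share q of affected participants also has a pre-treatment visit while the hemorrhage is present, the share found is q + (1 − q)f:

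| q (assumed) | Found | Missed |
|---|---|---|
| 0.25 | 28-45% | 55-72% |
| 0.50 | 52-63% (3-19 participants) | 37-48% |

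This treats every affected participant as having a hemorrhage; detachment is not modelled. It also ignores the 15% attrition assumed in 6.2.

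**Precision**

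With 1:1 arms, the 95% CI for a hazard ratio multiplies and divides the estimate by exp(1.96 × 2/√events):

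| Events | Factor |
|---|---|
| 6 | 5.0 |
| 8 | 4.0 |
| 19 | 2.5 |
| 30 | 2.0 |

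Full ascertainment of 6-30 events therefore still leaves a factor of 5.0 to 2.0.

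**The case against.** The strongest reply is that the plan needs only a clarification. The parent trial may record between-visit eye events, and the laboratory outcomes suggest that parent data will be used anyway. The introduction to section 6 promises a detailed analysis plan before study completion, which could name the parent database. Two uncommon events would mainly be tabulated. The 1.8D wording could bring in a vitrectomy done for hemorrhage or detachment. Treated disease also reaches the analysis through the efficacy composite and visual acuity outcomes. Site training and monitoring (7.3) may limit differences in how sites read the rule.

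Much of this is fair. The parent protocol is not among the documents, so a reader should not infer that these events go unrecorded everywhere; the gap is that this plan does not bring them in. Differing site interpretations are possible but not shown. The looser-reading percentages rest on assumptions throughout and should not be read as forecasts.

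Two things stand against it. A later analysis plan can name an existing data source, but it cannot recover an interval history that nobody took at the 2-year visit. And section 6.4 goes beyond tabulation: it calls for a comparison between arms with adjusted P-values, on events defined by the visit-day rule.

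**Conclusion.** The concern holds as a mismatch between a named outcome and its collection rule. Followed literally, the rule gives a nearly empty comparison: about 0.14-0.22% of follow-up is covered, and fewer than 0.1 recorded onsets are expected at the assumed 1-5% incidence. Under looser readings the loss ranges from over 90% to a little over a third, depending on assumed incidence, visibility and treatment-visit shares. Confidence is high on the wording and low on the size of the loss under those readings.

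A reader might infer a bias between arms. The documents do not support that: the rule is the same in both randomized arms, so the expected effect is lost events and lost precision. Nor is the primary outcome affected, because it has its own components and collects treatment at any time. The practical risk is that low counts are mistaken for reassurance. This should be fixed, because an interval history not taken at a visit is difficult to recover later.

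**What to change.** - In 1.8E, 1.8F, 1.9, 4.3 and 6.4, define the outcome as any vitreous hemorrhage or retinal detachment in a study eye from enrollment in the ancillary study to last contact.
- Add one interval-history item at the existing 2-year, 4-year or closeout, and pre-treatment visits; 4.2 can say so.
- Supplement it with parent-trial adverse event records where available, counting each participant once.
- Name the sources in 6.4 and report participants with an event by arm, with a confidence interval.
- Reconcile 1.8D with 3.1 and the schedule on what triggers the pre-treatment visit.
- If outside records are to be used for diagnoses, widen the release described in 3.1 beyond treatment.

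If between-visit events will not be collected, drop the comparison between arms and state that the counts cover visit-day events only.

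The cost is one case report form item, the wording changes, and IRB review of the amendment, with a decision on re-consent if the consent form changes (8.2). A data transfer from the parent trial may be needed; its effort cannot be judged from these documents. The main weakness is recall error, in both the diagnosis and its date. No new visits or procedures are required.
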